6.0 Treatment Plan

Subjects meeting the eligibility requirements in Section 4.1 and who have given signed informed consent will start the treatment dose of Vandetanib 300 mg or placebo orally, daily, starting such time as to allow 7 to 14 doses with the 7th or 14th dose given on the morning of the operation. Patients will return to clinic the day before the scheduled operation or the morning of surgery for repeat laboratory studies and EKG. Costs of the post-treatment labs and EKG will be covered by the PI. The results will be reviewed and safety to proceed documented prior to the operation. The study calendar (which will be provided at the pretreatment office visit to document administration of the study drug and any side effects associated with treatment) will be reviewed, pill counts performed, and an adverse events assessment performed at that time. Any concerns related to toxicities and safety to proceed to surgery will be addressed with the attending surgeon at that time. Common induction anesthetics (isoflurane, desflurane and sevoflurane) can cause QTc prolongation. Any QTc (>440 ms) on EKG should be discussed with the attending anesthesiologist prior to induction, and these induction agents should not be used if QTc > 480 ms. A flow chart of the preoperative screening procedure is shown in appendix 3. Subjects will be instructed to take their medication at the same time each day. In general subjects should take their dose every day even if it is not at the recommended time. Specific questions regarding timing and doses can be directed to [name] [contact], [name]). Patients will be removed from the study for failure to take at least 80% of the study doses. Patients will not be replaced if they are removed from the trial.

Women of Childbearing Potential (WOCBP) must use *highly effective* methods of birth control (one method or a combination of methods that results in a less than 1% failure rate per year) throughout therapy and must maintain full contraception for at least 95 days after the last dose of Vandetanib.

7.0 Drug Formulation, Availability and Preparation

7.1 Vandetanib

Availability

AstraZeneca Pharmaceuticals Investigational Products will pack, label, and supply the investigational product (IP) for this study. Tablets will be packed into white high-density polythene bottles with child resistant, tamper evident closures. Study drug must be kept out of the reach of children. Each bottle will contain 100 tablets. Patients will be supplied with sufficient amounts of tablets at each dispensing visit plus overage (2 week supply with 2 additional doses). Drug and placebo will be sent to the Investigational Drug Service (IDS) in the Department of Pharmaceutical Care at the University of Iowa. The IDS will perform randomization using randomization.com and provide identical packages of drug or placebo for distribution by the pharmacist in the cancer center. Randomization will not be stratified and will be performed in groups of eight patients and for the entire cohort. Packages will be sequentially numbered and distributed as patients are enrolled, such that when a patient is enrolled they will be given the lowest numbered package remaining. Package number and patient identification number will be recorded in the study database, and the package key will held by the IDS and released to the investigator on completion of the trial.

Vandetanib tablets must be taken whole or dispersed in water, without crushing. If tablets cannot be taken whole, the tablets can be dispersed in a glass containing 60 mL of non-carbonated water and stirred for approximately 10 minutes until the tablets are dispersed (will not completely dissolve). No other liquids should be used. The mixture should be swallowed immediately. To ensure the full dose is received, the patient should refill the glass with an additional half glass of water and mix with any remaining drug and drink it.

There are no food restrictions for the administration of Vandetanib tablets. Vandetanib tablets should be taken in the morning at about the same time each day with a glass of water.

The first dose of Vandetanib tablets will be taken only after all the assessments assigned have been performed. Patients should take study drug in the morning. If a patient inadvertently misses a dose and the next dose is in 12 hours or more, the patient should take the missed dose immediately and the next dose at the normal time. If it is less than 12 hours before the next dose, the patient should take the next dose at the normal time and the missed dose should not be taken. The missed dose must be documented in the CRF, where appropriate, with a comment indicating the patient missed the dose. The dose of study treatment may be repeated if vomiting occurs within 30 minutes of taking the study treatment. If vomiting occurs after 30 minutes of taking the study treatment, the dose will not be repeated.

Labels will be prepared in accordance with Good Manufacturing Practice (GMP) and local regulatory guidelines. The labels will fulfill GMP Annex 13 requirements for labeling.

Information on the bottle labels for Vandetanib will indicate the study number, contents, caution, and storage conditions and will have blank spaces for the patient number, visit number, and dispensing date (to be written in by the site personnel at the center at the time of dispensing). Instruction that study drug should be taken as directed will be included on the label. Patients will be supplied with a study participation card where the dosing instruction will be described for a patient by Investigator or delegate. All study drugs should be kept in a secure place under appropriate storage conditions

Administration

Subjects will be asked to take Vandetanib as a single oral daily dose of 300 mg or placebo. Patients will discontinue the drug and be removed from the study for toxicity. A patient may withdraw from the study at any time for any reason without prejudice for future treatment. Patients will be removed from the study for failure to comply with greater than 80% of scheduled doses.

Toxicity

The major toxicities of Vandetanib are nausea/vomiting/diarrhea, hypertension, thrombocytopenia, prolonged QT interval, Torsades de pointes, and ventricular tachycardia. The patients will be carefully screened for any conduction abnormalities, arrhythmia, electrolyte/coagulation/platelet abnormalities, and medications in Appendix 2 associated with QT prolongation. The short duration of treatment, two weeks, should limit toxicity. Detailed description of toxicities is provided in sections 11.2.3 and 11.2.4.

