1.2 Tyrosine Kinase Inhibitor Background

The receptor tyrosine kinases (RTK) are a family of molecules involved in receiving hormonal and chemokine signals and starting signal transduction pathways often involved in growth, cell survival, and proliferation. Activating mutations of RTK's have been identified in a wide variety of cancers including gastrointestinal stromal tumors (GIST), chronic myelogenous leukemia (CML) and medullary thyroid cancer (MTC), among others. Tyrosine kinase inhibitor (TKI) therapy has provided promising new targeted treatments for cancers driven by RTK activation.

The tyrosine kinase expression profile of breast cancers is a relatively new field. Since bevacizumab was developed, study of tyrosine kinase inhibition has focused on VEGFR antagonism and EGFR. More recently, expression of RET has been discovered in breast cancers with an association with estrogen receptor expression [3-6]. Mutations of the RET proto-oncogene are well described in MTC and the multiple endocrine neoplasia (MEN) 2 syndromes. Trials have been conducted in breast cancer with multiple TKI's without significant efficacy [7, 8]. However, these trials have focused primarily on ER negative cancers which express low levels of RET relative to estrogen receptor positive tumors, and metastatic tumors which are more likely to be ER negative.

In vitro, blocking RET activation, either by reducing protein levels, or with pharmacologic inhibition, leads to decreased activation of cellular mediators of proliferation and growth including ERK1/2 and AKT [9, 10]. Further it has been shown that inhibiting RET activation can restore sensitivity to Tamoxifen, prevent Tamoxifen resistance, and decrease cell proliferation in an ER and RET expressing breast cancer cell line [6]. Further, RET expression is a negative prognostic indicator in breast cancer [11]. We hypothesize that Vandetanib will be more efficacious in treating RET expressing breast cancers compared to breast cancers expressing lower levels of RET. Although there is a subset of ER-negative RET expressing tumors, most expression is associated with ER, making that the most likely phenotype to benefit from RET antagonist therapy.

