2.0 Study Objectives

- 2.1 Determine the change in Ki-67 expression on paired samples obtained before and after Vandetanib treatment.
- 2.2 Compare TUNEL levels and phosphorylation specific levels of ERK1/2, AKT, and mTOR levels in paired samples obtained before and after Vandetanib treatment.
- 2.3 Evaluate any differences in analyses 2.1 and 2.2 based on level of RET expression as well as between ER-positive and ER-negative tumors.

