4.3 Sample Size

This study will aim to accrue a total of 40 subjects with invasive breast cancer into both the placebo and treatment arms (80 patients in total). The diagnosis will be based on histopathological evidence. The number of subjects was chosen based on the estimated ability to provide meaningful information on breast cancer. For discussion of statistics and power analyses, please see Section 12.

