12.0 Statistical Analysis

In this study, women will be enrolled after core breast biopsy demonstrates invasive breast cancer. Baseline tissue sample will be obtained on study participants, after which, subjects will take Vandetanib or placebo until the time of a definitive surgical procedure, at which point the resection specimen will serve as a paired tissue sample. In vivo response Vandetanib will be assessed through analyses of the change in tissue levels of KI67, TUNEL, and changes in activation of ERK1/2, AKT, and mTOR and compared to placebo treated patients. All data points will be evaluated as paired continuous data points.

Descriptive statistics (means, medians, standard deviations, percentages, and confidence intervals) will be reported for all baseline and follow-up variables as well as for their changes over time. Statistical comparisons of the changes will be performed with paired t-test for continuous variables. Power analysis for comparisons of

continuous variables was based on published results for Ki-67 [20]— the only readily available results for the proposed treatment and study population. Based on a published standard deviation of 10%, the planned enrollment of 35 subjects will ensure 90% power to detect a decrease of 5% in Ki-67. The power drops to 82% if a two-sided alternative is considered. We will enroll 40 patients in each arm to account for non-compliance and withdrawal.

With a total of 70 evaluable patients (i.e. 35 in control and 35 in treatment group), we can achieve 70% power to detect 6% difference in Ki-67 between the two arms, from the null hypothesis that both arms have equal expression of Ki-67. In this case, we operate under the assumption that both arms have similar standard deviation of 10%, that the significance level is 5%, and that a two-sided two-sample t-test has been used. The power is 80% if a one-sided two-sample t-test is used under the same assumptions. We will enroll 80 patients (40 per arm) to account for potential patient dropouts and ineligibility for analysis due to missed doses.

Power in subgroup comparisons is likely to be low and, thus, the results are most useful for generating hypotheses to be tested in future studies. All statistical tests will be one-sided and assessed for significance at the 5% level.

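### The planned between-arm comparison of Ki-67 is unadjusted, which gives up precision and leaves chance ER imbalance uncorrected, although baseline Ki-67 and ER status are both collected

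*Combined protocol and SAP*

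**What the plan says.** **Allocation.** Section 7.1 states: "Randomization will not be stratified and will be performed in groups of eight patients and for the entire cohort". The aim in section 4.3 is to "accrue a total of 40 subjects with invasive breast cancer into both the placebo and treatment arms (80 patients in total"). Groups of eight balance the arm totals and not the tumour types, and section 4.0.1 admits every subtype of invasive disease.

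**Objectives.** Objective 2.1 concerns change in Ki-67 on paired samples. Objective 2.3 asks whether the results differ by RET level and "between ER-positive and ER-negative tumors". Section 1.2 hypothesises that response depends on RET expression and says of ER that "most expression is associated with ER, making that the most likely phenotype to benefit from RET antagonist therapy".

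**Analysis.** Section 12 assesses changes in the markers against placebo. It names a paired t-test for changes, and a two-sample t-test in the between-arm power text. It names no covariate, stratum or interaction term, and no method for objective 2.3. It does say that subgroup power will probably be low and that subgroup results serve to generate hypotheses.

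**Data available.** Ki-67 is measured on both samples (section 9.1). ER is a standard-of-care marker (section 9.2) and is marked at baseline in the section 5.0 schedule. A note to that table lets staging determinants come from either the baseline or the surgical sample.

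**The concern.** Two baseline measurements that could explain part of the variation in Ki-67 change are collected and then left out of the comparison between arms. Baseline Ki-67 is half of the paired measurement itself. ER is the phenotype that the rationale links to RET. With neither stratification nor adjustment, the ER mix of the two arms is left to chance, and nothing in the analysis corrects for the split that occurs.

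Precision is at stake in a trial with little to spare: section 12 gives 70% two-sided and 80% one-sided power for its 6-point difference. Objective 2.3 also has no stated analysis, so the estimate that will answer it is not fixed in advance.

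**Working it through.** **1. The plan's own power.** Inputs from section 12: "With a total of 70 evaluable patients (i.e. 35 in control and 35 in treatment group"), a 6-point difference, "both arms have similar standard deviation of 10"%, and a 5% level. The noncentrality is 6 / (10 × √(2/35)) = 6 / 2.390 = 2.51. The noncentral t distribution on 68 degrees of freedom gives 69.7% two-sided and 80.0% one-sided, so the stated 70% and 80% reproduce. The normal approximation used below gives Φ(2.51 − 1.645) = 80.7% one-sided. No stated power depends on ER.

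**2. How uneven the ER split could be.** The documents give no ER mix, so the counts are assumptions. With 40 per arm, the number of ER-negative patients in one arm is hypergeometric.

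| ER-negative of 80 (assumed) | Split or worse | Gap in ER share | Probability |
|---|---|---|---|
| 16 | 10:6 | 4/40 = 10 points | 0.402 |
| 16 | 11:5 | 6/40 = 15 points | 0.161 |
| 24 | 15:9 | 6/40 = 15 points | 0.222 |
| 24 | 16:8 | 8/40 = 20 points | 0.087 |

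If the ER counts are instead treated as binomial with an ER-positive share of 60-80%, a gap of at least 10 points has probability 33-42%, and a gap of at least 20 points 3.5-8.6%.

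**3. What a split does to the contrast.** Shift = gap in ER share × difference between ER groups in mean Ki-67 change. The second factor is assumed to be 5 or 10 points.
- 10-point gap: 0.10 × 5 = 0.5, or 0.10 × 10 = 1.0 points.
- 20-point gap: 0.20 × 5 = 1.0, or 0.20 × 10 = 2.0 points.

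The target is 6 points.

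**4. Gain from adjusting for ER.** Hold the total SD of change at 10, let p be the ER-positive share and G the ER gap in mean change. The residual variance is 100 − p(1 − p)G².

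| G (assumed) | p (assumed) | Residual SD | One-sided power, 6 points |
|---|---|---|---|
| 0 | any | 10.00 | 80.7% |
| 5 | 0.6 / 0.7 / 0.8 | 9.70 / 9.73 / 9.80 | 82.7% / 82.5% / 82.0% |
| 10 | 0.6 / 0.7 / 0.8 | 8.72 / 8.89 / 9.17 | 89.1% / 88.1% / 86.3% |

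**5. Gain from adjusting for baseline Ki-67.** Assume equal variance σ² before and after, and correlation r. The variance of change is 2σ²(1 − r) = 100. The residual variance after adjustment is σ²(1 − r²) = 50(1 + r).
- r = 0.7: variance 85, SD 9.22, power 86%.
- r = 0.3: variance 65, SD 8.06, power 93%.

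Steps 4 and 5 are separate calculations. ER and baseline Ki-67 may overlap, so the two gains should not be added.

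**6. What stratified allocation would add for objective 2.3.** With 16 ER-negative and 64 ER-positive patients and SD 10, the standard error of the ER-by-treatment difference is:
- even split: 10 × √(2/8 + 2/32) = 5.59;
- 11:5 split: 10 × √(1/11 + 1/5 + 1/29 + 1/35) = 5.95, about 6% wider.

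Averaged over chance splits with 35 evaluable per arm, stratifying raises power for a 10-point interaction from 48.7% to 50.4% when 80% are ER-positive. The gain is smaller at 60% and 70%.

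**The case against.** The strongest defence is that nothing here is invalid. Unstratified randomisation is unbiased, the t-test's standard error already allows for chance imbalance, all stated powers reproduce, and the plan already treats subgroup results as hypothesis-generating. All of that stands. It limits the point to efficiency and prespecification, but it does not explain why data already in hand should go unused.

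A reader might infer more than the documents support, in five ways:

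- **That the shift could rival the 6-point target.** This comes from applying an ER gap in Ki-67 level. Section 12 analyses paired change, which removes a stable level difference between ER groups. The power text's null, "from the null hypothesis that both arms have equal expression of Ki-67", does read as level, but that is loose wording and not a second analysis. A 30-point level gap with 20% ER-negative would by itself imply an SD of 30 × √(0.2 × 0.8) = 12, above the plan's 10 if that SD applied to levels.
- **That ER is the named driver of response.** Section 1.2 gives that role to RET; ER is the associated phenotype.
- **That lack of stratification is what undermines objective 2.3.** The main limit is the total number of ER-negative tumours, which stratification does not change (step 6).
- **That ER is certain to be known at allocation.** The standard-of-care assay and the baseline mark make it likely, but the table note stops short of guaranteeing it.
- **That the disclosed group size of eight is part of the problem.** Packages are identical and sequentially numbered, the pharmacy holds the key until completion, and the endpoint is a laboratory percentage. No route from guessing allocations to ER imbalance is shown.

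**Conclusion.** The point holds as an avoidable loss of precision and a gap in prespecification. It is neither a bias nor a type I error problem, and no stated figure is wrong. Chance imbalance of 10 points or more in ER share is quite likely (about 33-42% across the assumed mixes), but its effect on the change contrast is modest at about 0.5-2 points. The stronger argument is power. Against about 81% one-sided, ER adjustment gives 82-83% for an assumed 5-point ER gap in change and 86-89% for 10 points. Baseline Ki-67 alone gives about 86-93% for assumed pre-post correlations of 0.7 to 0.3. If ER does not predict change, ER adjustment gains essentially nothing and costs one degree of freedom.

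These sizes rest on the assumed ER mix, ER gap and correlation, on equal pre and post variances for the baseline calculation, and on reading the SD of 10 as the SD of change. None of these is settled by the documents.

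**What to change.** Before unblinding, make these changes in section 12:

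1. Replace the unadjusted between-arm t-test with a linear model (ANCOVA) of Ki-67 change on arm, with baseline Ki-67 and ER status as covariates. Use the core-biopsy ER result where available, since the surgical sample is taken after treatment, and state what is used when it is missing. With baseline Ki-67 in the model, the arm estimate is the same whether the outcome is change or surgical-sample level, which also settles the loose wording of the null.
2. Report objective 2.3 as treatment-by-ER and treatment-by-RET interaction estimates with confidence intervals, labelled exploratory. State in advance how RET will be coded.

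The cost is SAP wording only: no extra patients, samples or assays.

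Optionally, if the list can still be redrawn and ER is available before randomisation, the pharmacy could keep separate package sequences for ER-positive and ER-negative patients. This needs two lists and may leave the arm totals a few apart through unfilled groups. It adds at most about 2 points of power for objective 2.3, so the analysis change should come first.

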8.0 Ancillary Therapy

Because Vandetanib is metabolized by P450 CYP3A4 enzyme, drugs that affect metabolism by this enzyme may alter Vandetanib levels and enhance toxicity. Agents that inhibit CYP3A4 include: erythromycin, cyclosporine, fluconazole, itraconazole, ketoconazole, and grapefruit juice. For these reasons these drugs and foods should be avoided, if at all possible, during the Vandetanib treatment. See List of CYP3A4 inhibitors in Appendix 1. Vandetanib can also cause prolongation of the QTc and Torsades de Pointes. Medications that cause prolonged QTc are listed in Appendix 2 and should be avoided while on study, and patients will be excluded if they take any of the listed medications. Patients will also be instructed to avoid initiation of any of these compounds while on study. Concomitant medications will be reviewed at the time of study entry and at the time of scheduled assessments and procedure, to assess use of agents to avoid, but ongoing documentation is not required in this study.

9.0 Criteria for Response

The primary study end point will be down regulation of proliferative index measured by Ki-67 expression.

9.1 Ki-67

Tissue samples from the paired baseline and endpoint samples will be sent to the Histology Research Laboratory and percentage of cells expressing K-67 will be determined by immunohistochemical staining. The FFPE tissue blocks from core biopsies performed at other hospitals will be obtained and analysis for study data points will be performed and interpreted in the pathology laboratory at UIHC.

9.2. Other tumor markers

ER, PR, and HER2 levels will be assessed per normal procedure by the department of pathology, which is standard of care for the diagnosis and treatment of breast cancer. RET, TUNEL, and phosphorylation specific levels of ERK1/2, AKT, and mTOR will also be assessed on the paired samples using immunohistochemical staining. If alternative assays are found to be more effective at evaluating the levels of these markers in the paired samples, they could be employed on these tissue samples as well. All costs of analysis not considered standard of care will be covered by the PI. Laboratory testing will be performed in the department of pathology histology lab [name]. Cost for assays will be covered by the PI through a HCC MOG grant. All specimens will be processed in the histology lab per standard of care with formalin fixation and paraffin embedding followed by routine clinical testing (ER, PR, HER2).

9.3 Follow-up Post Surgery

After surgery, the subject will return to clinic for a post-operative visit. This will involve a final drug toxicity evaluation. This is also the standard of care post-operative follow-up visit.

